Plan for statistical analysis	
Statistical analyses will be of explorative and descriptive nature. The study is not aimed to confirm or reject pre-defined hypotheses.
 
All variables will be analyzed descriptively with appropriate statistical methods: categorical variables by frequency tables (absolute and relative frequencies) and continuous variables by sample statistics (i.e. mean, standard deviation, minimum, median, quartiles and maximum). Continuous variables will be described by absolute value and as change from baseline per analysis time point, if applicable.
 
The variability of biomarkers assumed to be normal distributed will be analyzed using a linear mixed effect model with subject as random factor, and time as fixed factor, possibly including additional covariates as may result from the assessment at baseline for subject stratification or as required for clinical interpretation. Based on this model, point estimates (LS-Means) and exploratory 90% confidence intervals will be calculated for comparing baseline and 3 months data. For biomarkers assumed to be log-normal distributed, the logarithms of the biomarker concentration will be analyzed, and results will be reported as ratio for comparing baseline and 3 months data.
 
All analyses will be performed for the total study population (overall analysis). Subjects wearing at least once the VitalPatch biosensor system and for which data was successfully collected over 5 days will be included in the analysis.
 
Sample size and disposition information by analysis time point will be displayed in a frequency table.

 Replacement of AVIVO MPM with VitalPatch Biosensor as per Amendment 2 (Section 15.2)

 Replacement of AVIVO MPM with VitalPatch Biosensor as per Amendment 2 (Section 15.2)

 Adapted to reflect the extension on non-hospitalized subjects as per Amendment 3 (Section 15.3)

 Adapted to reflect the limitations of the VitalPatch biosensor system as per Amendment 3 (Section 15.3)

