### Secondary objectives:

- Association between VitalPatch biosensor and DynaPort Move Monitor data (e.g. different levels of activity) to adverse events/clinical outcome data occurring during the study period
- Assess the baseline level and longitudinal changes over time of heart rate, respiratory rate and ECG-derived parameters and the average of person-to-person physiological variability and the within-patient standard deviation between the baseline and 3-month measurements
- Assess the feasibility of activity tracking with two devices (VitalPatch biosensor and DynaPort Move Monitor) in patients with heart failure
- Correlation of activity data between VitalPatch biosensor data on activity and DynaPort Move Monitor
- Evaluate the relationship between physical activity levels, heart rate, respiratory rate and ECG-derived parameters and important measures in HFpEF; such as quality of life (QoL), patient reported outcome (PRO), biomarkers, outcomes (e.g. clinical endpoints such as hospitalization for heart failure, cardiovascular death, emergency visits)
- Support the development of HFpEF specific questions (PRO) for testing/validating cross-sectional and longitudinally
- Determine the variability of device derived biomarkers between subjects and within subjects over time in order to validate such biomarkers for clinical use in the context of heart failure
- Evaluate hs-copeptin as potential biomarker 
- Correlation between patch monitor collected data and inpatient clinical data during hospital stay (e.g. echocardiography, weight gain/loss, NYHA, heart rate)
- Explore the relationship between PA, 6MWD, PRO, biomarkers, adverse events/clinical outcomes
- Investigate the accuracy of patients' self-reports (PRO, e.g. KCCQ) of time spent on PA in real life vs. objective assessment by the DynaPort Move Monitor and VitalPatch biosensor

---

 Replacement of AVIVO MPM with VitalPatch Biosensor as per Amendment 2 (Section 15.2)

 Tissue impedance deleted as per Amendment 3 (Section 15.3)

 Replacement of AVIVO MPM with VitalPatch Biosensor as per Amendment 2 (Section 15.2)

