### **6.3 Justification of selection criteria**

Bayer develops several investigational medicinal products for the indication HFpEF for which until now no successful treatment is available. Until now all endpoints failed and were not predictive for the outcome of the patient's disease progression. Bayer intends to develop new endpoints and variables, which later might be useful to monitor pharmacodynamics effects and for the prediction of disease progression in interventional studies with new drugs.

Digital device-derived biomarkers are of high interest regarding the identification of new potential endpoints, especially for patient populations where no predictable biomarkers are available.

The new European guidelines (2016) for heart failure (HF) include the concept of HF with intermediate left ventricular ejection fraction (heart failure with mid-range ejection fraction, HFmrEF), i.e. an LVEF between 40 and 49%. However, a substantial heterogeneity may exist within patients with HFmrEF. In particular, this group may include both patients with de novo HF and patients with HF with previously reduced LVEF who have recovered their systolic function. Furthermore, considering the technical variability of echocardiographic assessment of ejection fraction as well as the biological variability, patients within the mid-range ejection fraction may represent patients with HFpEF as well as HFrEF. For the purpose of this study, it is critical to study well defined patient groups with either HFpEF or HFrEF to avoid a relevant overlap between both groups. Therefore, the inclusion criteria with respect to ejection fraction differ from current guidelines slightly. However, cut-off values used in the present study have also been used in several previous studies in patients with heart failure.

This study serves as a pilot study to identify a baseline for several digital biomarkers in HFpEF patients. In parallel some HFrEF patients are included for which a baseline for some of the device readouts is already available derived from studies with implantable cardioverter-defibrillator and cardiac resynchronization therapy devices. They serve as internal plausibility control.

Therefore, it is essential to include HFpEF and HFrEF patients in this study.

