Estimates from the model will be used to quantify the ability of a parameter to measure clinically relevant changes over time. The intraclass correlation coefficient (ICC) will be used as key statistic when considering the relative proportion of within- and between-individual variation is the expected correlation among measurements from the same individual, it can indicate the degree of difference between individuals and will also be used as measure reliability (ability to reflect true between-individual differences). For any sample, the ICC will be calculated with estimates from LMMs of both between-individual variance and within-individual variance, according the following:

$$ICC = \tau^2 / (\tau^2 + \sigma^2)$$

---

 Replacement of AVIVO MPM with VitalPatch Biosensor as per Amendment 2 (Section 15.2)

where  $\tau^2$  is a commonly used symbol for between-individual variance (variance of  $S_{0s}$  term in in the base model above) and  $\sigma^2$  for within-individual variance (variance of  $\varepsilon_{st}$  in the base model). Then, ICC will be the proportion of total variance ( $\tau^2 + \sigma^2$ ) attributable to between-individual differences ( $\tau^2$ ).

In addition, point estimates (LS-Means) and exploratory 90% confidence intervals will be calculated for comparing baseline and 3 months data by HF type (preserved/reduced), and may include intermediate time points if available.

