### 10.3.3.2 Analysis of correlations - amended

Given the high degree of collinearity expected within each set of data, multivariate approaches will be considered in order to take in account the covariance structure and properly assess simultaneously the correlation of variables within and between datasets consisting of multiple variables, such as digital or biomarker datasets.

The relationship between variables as obtained from a given source or technology will be assessed by means of Canonical Correlation. This analysis allows investigating the relationship between two multivariate sets of variables, such as the one obtained using the VitalPatch biosensor or DynaPort Move Monitor device, and another one as obtained from other contexts, such as contexts defined by the following data sets: i) echocardiography parameters set, ii) 12-lead ECG parameters set, and iii) a composite set including biomarkers, 6MWD score, KCCQ total score, and vital signs (blood pressure, heart rate). Such model will possibly indicate which combination of the many parameters observed using the device will better reflect a clinical context as given by ECG, KCCQ, or other data.

The correlation of digital biomarkers and AEs or concomitant medication (CM) will be tested by means of partial least square analysis (PLS-DA). The Y-matrix to use for PLS-DA regression can be – depending on the resulting complexity – i) a joint matrix of AEs and CMs; ii) grouping variable identifying subjects with similar AE and CMs (the latter obtained by multiple correspondence analysis and kernel based clustering). Such model will possibly indicate which combination of the many parameters observed using the device will better reflect a clinical profile as obtained from observed frequencies in AEs and CMs.

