## 10.4 Determination of sample size

Due to the exploratory nature of this study, the number and the diversity of parameters used to measure physical activity, or which could affect this outcome in “real-life” conditions, no modeling for power estimation was performed. The number of subjects was set to be comparable to other studies which involved the assessment of physical activity on daily life (activity monitoring) and where a significant difference in PA was observed (60 subject in

---

 Replacement of AVIVO MPM with VitalPatch Biosensor as per Amendment 2 (Section 15.2)

average). Also considering the expected variability due to measurement under unstandardized conditions [12] a number of 80 subjects (HFpEF n=60, HFrEF n=20) who completed the main study (i.e. visit 4) was defined as target.

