- Explore the relationship between PA, 6-minute walking distance (6MWD), PRO, biomarkers, adverse events/clinical outcomes
- Investigate the accuracy of patients' self-reports (PRO, e.g. KCCQ) of time spent on PA in real life vs. objective assessment by the DynaPort Move Monitor and VitalPatch biosensor³

¹ Will not be addressed due to change from AVIVO to VitalPatch (ECG data only)

² Will not be addressed due to change in procedure schedule

³ Meaningful assessment not possible given the provided variables.

Given the data situation (not all parameters provided by the vendor) and the low number of subjects (recruiting stopped early due to recruiting issues), not all the original objectives mentioned above will be addressed.

3. Study Design

This is a non-randomized, multi-center, observatory prospective patient study. The study will be conducted in several centers in EU and non-EU.

[figure not shown]
Patients hospitalized due to heart failure as well as ambulatory patients with heart failure will be included in this study. Overall approx. 80 subjects have to complete at least all device monitoring periods:

- Approx. 60 subjects with established diagnosis of heart failure with preserved ejection fraction (HFpEF; EF ≥ 45%) (Cohort 1) and
- Approx. 20 subjects with established diagnosis of heart failure with reduced ejection fraction (HFrEF; EF ≤ 35%) (Cohort 2).

All patients will receive the AVIVO / VitalPatch biosensor at 5 monitoring periods (5 patches each subject in total, monitoring period 7 / 5 days each period) and the DynaPort Move Monitor (belt) at 2 monitoring periods (7 day monitoring each period). Results from both devices are not visible to investigator and subjects to avoid bias on treatment decisions.

Biomarkers will be investigated during the hospital stay (only in case patient is hospitalized), at visit 1, and at visit 4. A 6-minute walking test will be performed at visit 1 / discharge and after 11-12 weeks.

Design overview

Abbreviations: KCCQ = Kansas City Cardiomyopathy Questionnaire score; QS = Questionnaire for patient reported outcomes (daily and weekly); 6MWD = 6 minute walking distance; FUP = follow up visit

4. General Statistical Considerations

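### The ICC is defined from a model without HF type, so it describes a mixed HFpEF/HFrEF population rather than reliability within HFpEF (minor)

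*Protocol*

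**What the plan says.** **ICC.** Protocol 10.3.3.1 writes a base mixed model with time as fixed effect and subject as random intercept. It then writes an extended model in which HF type (preserved or reduced) acts on intercept and slope. The ICC is τ²/(τ² + σ²). τ² is identified as the variance of the subject "term in in the base model above", and σ² as that model's residual variance. The section treats the ICC as its key statistic for within- and between-individual variation and as a measure of reliability. The least-squares means in the same section are requested by HF type; the ICC is not.

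**Canonical correlation.** Protocol 10.3.3.2 relates device data to an echocardiography set, an ECG set and a composite set: "This analysis allows investigating the relationship between two multivariate sets of variables". It mentions neither a split nor an adjustment by HF type. The synopsis sets the default: "All analyses will be performed for the total study population (overall analysis)". Protocol 10.1 also names the overall full analysis set, with a possible split by country, but promises particular attention to ejection fraction (EF) as a stratification factor. Section 10.3 says HF type will be considered.

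**Population and purpose.** The target is "a number of 80 subjects (HFpEF n=60, HFrEF n=20)". The two types are kept apart on purpose; section 6.3 says "it is critical to study well defined patient groups with either HFpEF or HFrEF to avoid a relevant overlap between both groups". The stated aim is endpoints for future HFpEF trials, and one secondary objective relates activity, heart rate, respiratory rate and "ECG-derived parameters and important measures in HFpEF".

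**SAP.** The SAP keeps the device-variability objective (section 2) but describes no ICC and no canonical correlation. It says the protocol analyses were comprehensively revised (7.2) and that recruitment stopped early (section 2). Patch data go to biomarker analyses that it does not describe (4.1). Its DynaPort mixed model has no cohort term (6.5.4.1).

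**The concern.** An ICC is high when subjects differ from one another by much more than they vary from visit to visit. In a pooled sample, part of the difference between subjects can simply be that some have HFpEF and some HFrEF. A single-type trial has no such component. A parameter that mainly tells the two types apart would therefore look more reliable here than it would in an HFpEF trial. The figure would also change if the types were enrolled in a different ratio. Because the study is meant to inform the choice of HFpEF endpoints, the within-HFpEF value is the one needed, and section 10.3.3.1 does not ask for it.

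A related but weaker worry applies to 10.3.3.2. If the types differ on a device variable and also on a clinical variable, pooling produces a correlation between the two even when none exists inside either type.

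**Working it through.** **Inputs from the documents.** The plan is 60 HFpEF + 20 HFrEF = 80 completers (Protocol 10.4), so the HFrEF share is w = 20/80 = 0.25 and w(1 − w) = 0.1875. The plan has no power figure to reproduce, since "no modeling for power estimation was performed".

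**Assumption.** D is the difference in means between HF types, in units of the within-type total SD. The documents do not give it, so a range from 0 to 1.5 is used.

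**Pooled ICC.** Set the within-type total variance to 1, so that τ² equals the within-type ICC. Leaving HF type out adds w(1 − w)D² to τ²:

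pooled ICC = (ICC_within + 0.1875 D²) / (1 + 0.1875 D²)

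For ICC_within = 0.60:
- D = 0: 0.60
- D = 0.5: (0.60 + 0.0469)/1.0469 = 0.618
- D = 1.0: (0.60 + 0.1875)/1.1875 = 0.663
- D = 1.5: (0.60 + 0.4219)/1.4219 = 0.719

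For other within-type values at D = 0.5, 1.0 and 1.5:
- 0.30 becomes 0.33, 0.41, 0.51
- 0.50 becomes 0.52, 0.58, 0.65
- 0.70 becomes 0.71, 0.75, 0.79
- 0.90 becomes 0.90, 0.92, 0.93

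**Dependence on the mix.** With equal numbers of each type, w(1 − w) = 0.25. At D = 1.0 the same parameter would give (0.60 + 0.25)/1.25 = 0.68 instead of 0.66, with nothing changed inside either type.

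**Simulation check** (60 + 20 subjects, two visits, 3,000 runs). With a true within-type ICC of 0.50, the base model averages 0.517, 0.574 and 0.645 at D = 0.5, 1.0 and 1.5; with HF type as a fixed effect the average is 0.49 to 0.50 throughout. With a true 0.70, the base model gives 0.710, 0.742 and 0.786, and the model with HF type 0.69 to 0.70.

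**Pooled correlation with none within type.** For differences Dx in the device variable and Dy in the clinical variable:

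r = 0.1875 Dx Dy / √[(1 + 0.1875 Dx²)(1 + 0.1875 Dy²)]

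- Dx = 0.5: r = 0.08 at Dy = 1 and 0.17 at Dy = 3
- Dx = 1.0: r = 0.16 and 0.32
- Dx = 1.5: r = 0.22 and 0.43
- Dx = 0 or Dy = 0: r = 0

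In a simulation with an assumed 5 + 5 variables, n = 80 and Dy = 3 on one clinical variable, the first canonical correlation averages 0.41 by chance alone. Pooled, it averages 0.42, 0.47 and 0.53 at Dx = 0.5, 1.0 and 1.5. Centred by HF type, it stays at 0.41.

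**The case against.** **The pooled ICC is not miscalculated.** The protocol defines reliability as the ability to reflect true differences between individuals, and a difference between types is one. The variability objective refers to heart failure in general. This stands: the pooled value answers a mixed-population question. It does not answer the HFpEF question.

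**The effect may be small.** At D = 0.5 the shift is about 0.02 for an ICC of 0.60. The sampling error of that ICC with 80 subjects and two visits is roughly (1 − 0.60²)/√79 = 0.07. This stands too. Only differences near 1 SD or more matter in practice.

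**HF type is partly handled.** The extended model contains it, the base model may be extended as appropriate, and 10.1 and 10.3 point towards using it. None of these statements is tied to the ICC, which is explicitly linked to the base model.

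**The SAP carries neither analysis forward.** This limits the point to the protocol text and to the biomarker analyses that the SAP leaves unspecified, for which protocol 10.3.3 is the only description given.

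A reader might infer more than the documents support:
- *That the EF gap is itself counted as reliability.* It is not. Only a type difference in the parameter being analysed enters τ². Eligibility EF may come from any imaging within 12 months before inclusion, so the Visit 1 echocardiogram need not respect the gap.
- *That the plan decides to pool the canonical correlations.* This follows only from silence combined with the overall-analysis default.
- *That parameters will be ranked wrongly.* For a within-type ICC of 0.55 to overtake 0.65 with no type difference, 0.1875 D² must exceed 0.10/0.35 = 0.286, so D must be above about 1.23.
- *That false device–clinical associations will be declared at some known rate.* The plan names no test for the canonical correlations, so no such rate can be assigned to it.

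**Conclusion.** The point holds in a limited form and is minor. As written, the ICC comes from a model without HF type, so it includes 0.1875 × D² at the planned mix and varies with that mix. No reliability figure within HFpEF is specified, although HFpEF is the population of the future trials.

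The size rests wholly on an assumed D. For a within-type ICC of 0.60 the rise is nil at D = 0, about 0.02 at 0.5, 0.06 at 1.0 and 0.12 at 1.5. It also rests on the planned 60:20 split. The SAP reports early stopping without final numbers, so the achieved weight w(1 − w) may differ from 0.1875.

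The canonical-correlation part is a lesser remark. It needs a type difference in both variable sets, and the pooling is inferred, not stated.

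**What to change.** Wherever the ICC is still computed, including the biomarker analyses mentioned in SAP 4.1, take τ² and σ² from a model with HF type and HF type × visit as fixed effects. HF type has only two levels, so a random-effect variance for it, as in the protocol's extended model, would be poorly determined. Let τ² and σ² differ by type, or fit the two types separately, and report the ICC for HFpEF and for HFrEF with 90% intervals. Keep the pooled ICC as secondary, labelled as describing the enrolled mix.

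If the canonical correlations are run, add a result with both variable sets centred by HF type, or one in HFpEF only.

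The cost is a few lines of code and one degree of freedom per variable for the centring. The HFrEF interval will be wide. For an observed ICC of 0.60 with two visits, the variance ratio is (1 + 0.60)/(1 − 0.60) = 4. Dividing and multiplying it by the 95% point of F, and converting each limit by (F − 1)/(F + 1), gives the 90% interval. With 20 patients (F = 2.168) it is about 0.30 to 0.79; with 60 (F = 1.540) it is about 0.44 to 0.72. With the lower recruitment that the SAP reports, the intervals would be wider if fewer patients of each type are available.

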### 10.3.3.2 Analysis of correlations - amended

Given the high degree of collinearity expected within each set of data, multivariate approaches will be considered in order to take in account the covariance structure and properly assess simultaneously the correlation of variables within and between datasets consisting of multiple variables, such as digital or biomarker datasets.

The relationship between variables as obtained from a given source or technology will be assessed by means of Canonical Correlation. This analysis allows investigating the relationship between two multivariate sets of variables, such as the one obtained using the VitalPatch biosensor or DynaPort Move Monitor device, and another one as obtained from other contexts, such as contexts defined by the following data sets: i) echocardiography parameters set, ii) 12-lead ECG parameters set, and iii) a composite set including biomarkers, 6MWD score, KCCQ total score, and vital signs (blood pressure, heart rate). Such model will possibly indicate which combination of the many parameters observed using the device will better reflect a clinical context as given by ECG, KCCQ, or other data.

The correlation of digital biomarkers and AEs or concomitant medication (CM) will be tested by means of partial least square analysis (PLS-DA). The Y-matrix to use for PLS-DA regression can be – depending on the resulting complexity – i) a joint matrix of AEs and CMs; ii) grouping variable identifying subjects with similar AE and CMs (the latter obtained by multiple correspondence analysis and kernel based clustering). Such model will possibly indicate which combination of the many parameters observed using the device will better reflect a clinical profile as obtained from observed frequencies in AEs and CMs.

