Number of subjects	Due to the exploratory nature of this study, and to the multiplicity and the type of the observed parameters, the number of target subject was chosen to be comparable with other studies where a significant difference in PA was observed. The study will enroll enough subjects to have 80 subjects (HFpEF n=60, HFrEF n=20) who completed the main study, i.e. visit 4.
Primary variable(s)	Daily physical activity (amount, intensity, duration) obtained from the VitalPatch biosensor  / DynaPort Move Monitor device
Time point/frame of measurement for primary variable(s)	Baseline level and longitudinal changes over time of physical activity and the average of person-to-person physiological variability and the within-subject standard deviation between the baseline and 3-month post baseline measurements. 

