## 9.7 Other procedures and variables

### 9.7.1 VitalPatch biosensor/DynaPort Move Monitor devices - amended

#### VitalPatch biosensor

VitalPatch biosensor will be provided by Bayer to sites. Subjects will wear the VitalPatch biosensor for overall 5 periods of 5 days each (for details on time periods see [Table 9–1](#)).

Parameters obtained from the VitalPatch biosensor are:

- ECG and parameters derived from ECG, like e.g. heart rate, HRV, AF burden, arrhythmias etc.
- Respiratory rate
- Skin temperature
- Step count
- Physical activity (duration and intensity)
- Posture

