**1. Physical activity**

- Type of activity
- Transitions between type of activity
- Steps
- Movement duration
- Movement frequency
- Movement intensity

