4.1 General Principles

The statistical evaluation will be performed by using the software package SAS release 9.4 or higher (SAS Institute Inc., Cary, NC, USA).

All variables will be analyzed by descriptive statistical methods. The number of data available, mean, standard deviation, minimum, median, and maximum will be calculated for metric data. Frequency tables will be generated for categorical data.

The analysis will be based on the Clinical Pharmacology Standard (CLIPS), version 3.0 [2].

Tables and listings describing the impact of COVID-19 on the study will be created as appropriate. If needed, the onset of the COVID-19 pandemic will be considered as 11 MAR 2020 (date when the WHO declared the COVID-19 pandemic).

VitalPatch and AVIVO data will not be transferred to the clinical database and will be considered in the scope of the biomarker analyses.

All planned statistical analyses will be explorative. A confirmatory statistical analysis is not intended. Thus, no adjustment for the type I error level will be done.

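### Protocol 10.3.3.2 plans canonical correlation and PLS-DA with no cross-validation or permutation reference, so noise alone gives sizeable in-sample values, and the SAP does not say whether the methods survive.

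*Protocol*

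**What the plan says.** Protocol 10.3.3.2 relates a VitalPatch or DynaPort variable set to one of three clinical sets: echocardiography, 12-lead ECG, or a composite of biomarkers, 6MWD, KCCQ total score and vital signs. The relationship "will be assessed by means of Canonical Correlation". The link between digital biomarkers and adverse events or concomitant medication "will be tested by means of partial least square analysis (PLS-DA"). In both cases the purpose is to learn which combination of device parameters best reflects a clinical picture. The section expects strong collinearity within sets. It gives no rule for the number of components and no cross-validation, hold-out or permutation step.

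Protocol 10.1 leaves statistical details to the SAP. The SAP names neither method. SAP 4.1 says: "VitalPatch and AVIVO data will not be transferred to the clinical database and will be considered in the scope of the biomarker analyses". The SAP's only biomarker section, 6.5.3, gives descriptive statistics and plots. SAP section 2 refers to "the low number of subjects (recruiting stopped early due to recruiting issues") and says that not all objectives will be addressed. Its footnotes drop three of them, but not the association of device data with adverse events and outcomes, nor the relationship of activity, heart rate and ECG-derived parameters to quality of life, PRO and biomarkers. SAP 7.2 says the protocol's analyses were comprehensively revised.

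**The concern.** Canonical correlation picks the weighted sum of device variables and the weighted sum of clinical variables that correlate most strongly in the sample at hand. PLS-DA likewise builds components that separate the groups in that sample. With many variables and few patients, both return a substantial value when nothing is there. The study exists to nominate novel endpoints for future HFpEF trials. A reader who sees an in-sample correlation of 0.5 or 0.6 without a null reference cannot tell a candidate from noise, and combinations chosen this way may not replicate in the next trial.

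**Working it through.** **The plan's own figure.** There is none to reproduce. Protocol 10.4 says "no modeling for power estimation was performed", and no expected correlation is given.

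**Inputs**
- Patients: n = 80, from the Protocol synopsis ("The study will enroll enough subjects to have 80 subjects (HFpEF n=60, HFrEF n=20) who completed the main study").
- Patch variables, p = 10 (assumed): Protocol 9.7.1 begins its list with "ECG and parameters derived from ECG, like e.g. heart rate, HRV, AF burden, arrhythmias etc", which names four items. It adds respiratory rate, skin temperature, step count, activity duration, activity intensity and posture: 4 + 6 = 10. The list is open-ended.
- Patch variables, p = 4 (assumed): SAP section 2, footnote 1, describes the VitalPatch data as ECG only. Keeping just the four named ECG-derived items gives 4.
- DynaPort variables, p = 18: Protocol 9.7.1 lists 6 physical-activity items (one is "Transitions between type of activity"), 6 energy-expenditure items and 6 sleep items: 6 + 6 + 6 = 18, counting each item as one variable.
- Clinical variables, ECG set: q = 4 recorded parameters in Protocol 9.6.3 (HR, PR, QRS duration, QT), or 6 with the Bazett and Fridericia corrections.
- Clinical variables, composite set: q = 8, from 3 core biomarkers + 6MWD + KCCQ + systolic pressure + diastolic pressure + heart rate; or 8 + 4 = 12 with the four optional biomarkers.
- The echocardiography set is not enumerated, so it is not computed.

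**Method.** Draw independent standard normal X (n by p) and Y (n by q), centre each, and take orthonormal bases Qx and Qy. The first canonical correlation is the largest singular value of Qx'Qy. Average over at least 1,000 replicates. The true correlation is zero throughout.

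**A hand check.** With a single clinical variable, the null expectation of R-squared is p/(n-1). For p = 10 and n = 80 that is 10/79 = 0.127, whose square root is 0.36. Canonical correlation also optimises over the clinical side, so its values are higher.

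**Mean first canonical correlation under noise, n = 80**

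| Device variables | q = 4 | q = 6 | q = 8 | q = 12 |
|---|---|---|---|---|
| 4 (patch, ECG items only) | 0.35 | 0.40 | 0.45 | 0.51 |
| 10 (patch, Protocol 9.7.1) | 0.48 | 0.53 | 0.57 | 0.64 |
| 18 (DynaPort) | 0.60 | 0.65 | 0.68 | 0.74 |

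Repeat runs differ by up to about 0.01. The 5th to 95th percentile range is 0.50-0.65 for 10 by 8 and 0.68-0.80 for 18 by 12. Collinearity within a set does not change the result: with a within-set correlation of 0.7 in X, 10 by 8 still gives 0.575.

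**Other sample sizes (assumed)**
- n = 100: 0.52 (10 by 8) and 0.67 (18 by 12).
- n = 60: 0.66 and 0.83.
- n = 40: 0.79 and 0.95. With four patch variables, n = 40 gives 0.49 (q = 4) to 0.72 (q = 12).

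**PLS-DA on noise.** With a balanced binary outcome (assumed) and one or two components, the mean in-sample AUC at n = 80 is 0.69-0.70 for p = 10 and 0.75-0.77 for p = 18. At n = 40 it is 0.76-0.78 and 0.83-0.88.

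**What removes the inflation.** At n = 80, 5-fold cross-validation brings the mean null canonical correlation to about 0 (-0.02 for 10 by 8, 0.00 for 18 by 12). Ridge with penalty 1 on standardised variables, assessed in-sample, still gives 0.55 and 0.69.

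**The case against.** The strongest reply is that these analyses may no longer be planned. The protocol hands the details to the SAP, the SAP contains neither method, and it says the analyses were comprehensively revised. The biomarker work that receives the patch data is not described, so it cannot be assumed to use Protocol 10.3.3.2. This stands as a limit: the documents do not show that either method will be run at the reduced size. It does not close the point, because the SAP neither withdraws the methods nor gives another association method for the patch data, while several objectives that need one remain in its list.

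A second reply is that the study is an exploratory pilot with no confirmatory aim. That answers a complaint about type I error, which is not made here. A permutation or global test would be calibrated, but none is specified, and the inflated value would be read as an effect size.

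A reader might infer several stronger things that the documents do not support:
- **That 0.57-0.74 is the range for the patch analysis.** The 0.74 uses the 18-item belt list, and the SAP carries no set-to-set analysis for the belt. If the patch set is the four named ECG-derived items, every n = 80 value computed is below 0.57.
- **That 80 is a maximum.** It is a completer target with dropouts replaced (Protocol 6.4.2). A dropout with one successful patch period can enter the protocol's FAS, so n could exceed 80 and the values fall somewhat.
- **That the HFrEF cohort of 20 would be analysed alone, with correlations near 1.** No such analysis is specified.
- **That the missing penalty is the defect.** A penalty alone leaves most of the inflation in place.

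**Conclusion.** The point holds in limited form. As written, Protocol 10.3.3.2 would report in-sample canonical correlations and PLS-DA fits with no reference for what noise produces. At n = 80 that noise level is about 0.35-0.51 for four patch variables against 4-12 clinical variables, about 0.48-0.64 for ten, and up to 0.74 for 18 DynaPort items against 12. The PLS-DA noise AUC is about 0.69-0.77 for 10-18 device variables.

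These figures rest on assumed variable counts, and for PLS-DA also on a balanced binary outcome. The direction at a smaller sample is certain, but its size cannot be stated because the documents give no reduced n. Whether the problem reaches the report depends on the undescribed biomarker analyses keeping these methods. That is a gap for the sponsor to close, and the documents do not establish the answer either way.

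**What to change.** State in the SAP, or in the plan that governs the biomarker analyses, whether canonical correlation and PLS-DA are kept or withdrawn.

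If they are kept:
- List the variables in each set and fix the number of components, or the rule for choosing it within the cross-validation.
- Report only the cross-validated canonical correlation and the cross-validated PLS-DA error, each beside its permutation distribution.
- Do not present in-sample values as evidence for a candidate endpoint.

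A penalty is optional and is not sufficient alone. Replacing the joint methods with pairwise correlations is not required, since the protocol chose joint methods because it expects collinearity.

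The cost is a short text change, computing time and smaller reported correlations. No additional patients or measurements are needed.
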